1.2 SPECIFIC AIMS

Hypothesis: The initiation of LTLR-WB resuscitation in the prehospital setting with continuation through the in-hospital acute resuscitation phase of care will significantly reduce the morbidity and mortality attributable to hemorrhagic shock post-injury as compared to standard prehospital and in-hospital resuscitation practice.

Specific Aims:

Specific Aim I: Determine the feasibility and most appropriate study population that will lead to a large multicenter clinical trial designed to evaluate the effectiveness of prehospital through inhospital LTLR-WB as compared to standard care practice in patients at risk of hemorrhagic shock.

Specific Aim II: Determine if prehospital through in-hospital LTLR-WB reduces 28-day mortality, in-hospital mortality, multiple organ dysfunction, presenting coagulopathy, 24-hour resuscitation requirements and early mortality as compared to standard of care prehospital and in-hospital resuscitation in patients at risk of hemorrhagic shock.

Specific Aim III: Determine the primary drivers by which prehospital through in-hospital LTLR-WB improves clinical, resuscitative and hemostatic outcomes as compared to standard of care prehospital and in-hospital resuscitation in patients at risk of hemorrhagic shock.

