lactate and shock index (SI, heart rate/systolic blood pressure-bpm/mmHg) 4) Acute Respiratory Distress Syndrome (ARDS): We will compare pulmonary dysfunction using the Berlin definition for ARDS.⁸⁶ 5) Nosocomial Infection (NI): We will compare the incidence of pneumonia and blood stream infections. 6) Mortality: We will compare mortality rates at 3, 6 and 24 hours following arrival, all cause in-hospital and 28-day mortality. 7) Blood component transfusion and resuscitation requirements at 24 hours: We will compare overall blood component transfusion requirements and crystalloid/colloid resuscitation requirements across the two arms. 8) Acute Hemolytic Transfusion Reaction (AHTR): We will compare the incidence of AHTRs across study arms as defined by the CDC/National Healthcare Safety Network (NHSN) Hemovigilance Surveillance definition. (www.cdc.gov/nhsn) Length of hospital stay and intensive care unit stay. Length of stay and ICU resources will be descriptively compared. Patients will be followed for 28 days from admission for the 28-day mortality outcome utilizing chart review, patient contact or utilization of the social security death index for those who cannot be contacted.

Predefined Subgroup Analyses: Predefined subset analyses for the pilot trial will be performed looking at our primary outcomes (safety/efficacy and feasibility) in 1) Females > 50 years of age versus study cohort with females < 50 years excluded ; 2) Patients who ultimately did or did not require in-hospital blood transfusion; 3) Patients with and without significant traumatic brain injury (Head abbreviated injury score- AIS >2); 4) Patients enrolled from the scene of injury versus those enrolled from a referral hospital; 5) Patients that require operative intervention in the first 24 hours; 6) Those patients with a preinjury history of anticoagulation / antiplatelet therapy; 7) Patients who ultimately did or did not require massive transfusion (≥ 10 units blood in first 24 hrs) 8)Patients who did or did not receive prehospital PRBCs.

Clinical Outcome Definitions:

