Estimates for Trial Secondary Clinical Outcomes: We will estimate the mean differences in the average Denver post-injury MOF score derived from the 3 highest daily scores between two treatment groups as the main clinical outcome for the pilot trial. We will also record and compare the overall proportion of patients who developed MOF based on Denver score > 3 and compare MOF free days. Similarly, the incidence of ARDS, NI, mortality (6hr, 24hr and 28 day) and hemolytic transfusion reactions will be recorded. We will perform survival analysis for all mortality outcomes. Blood component and resuscitation volumes over the initial 24 hours, length of ICU stay, days on a ventilator, and total hospital stay will be also be determined. Estimated proportions and means and 95% confidence intervals will be created for each outcome using the data from the entire pilot trial (i.e. combining the data from the two assigned treatment arms). Absolute and relative differences for continuous levels and event rates by assigned treatment will be estimated and 95% confidence intervals will be calculated to identify potential treatment differences for safety and for study planning purposes. Subgroup analyses will be exploratory and be based on baseline factors specified prior to the initiation of the trial.

The Following Outcomes Will Be Recorded:

- 1. The average Denver post-injury MOF score derived from the 3 highest daily scores. Differences between these averages will be estimated across the study two arms.
- Proportion of patients who developed MOF based on Denver score > 3 and compare MOF free days across the study two arms.
- 3. The incidence of ARDS, NI, mortality (6hr, 24hr and 28 day) and hemolytic transfusion reactions will be recorded and compared across the study two arms
- 4. Survival analysis in relation to all causes of death.
- 5. Blood component and resuscitation volumes over the initial 24 hours,
- 6. Length of ICU stay, days on a ventilator, and total hospital stay will be also be determined.

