3.3 EXCLUSION CRITERIA

- 1. Documented age: Age ≥90 or <18 years of age
- 2. Inability to obtain intravenous or interosseous access
- 3. Isolated fall from standing injury mechanism
- 4. Known prisoner or known pregnancy
- 5. Traumatic arrest with > 5 minutes of CPR without return of vital signs
- 6. Brain matter exposed or penetrating brain injury (GSW)
- 7. Isolated drowning or hanging victims
- 8. Isolated burns without evidence of traumatic injury
- 9. Referral Hospital In-patient admission
- 10. Objection to study voiced by subject or family member at scene
- 11. Wearing PPOWER opt-out bracelet

Inclusion and exclusion criteria will be assessed based on available information at the time of enrollment. Although all reasonable efforts will be made by the air medical crew to either directly witness or obtain documentation of eligibility criteria, due to the nature of the emergency pre-hospital setting, there may be occasions where the air medical crew must rely on verbal report of inclusion criteria, including qualifying vitals, from the referring hospital or ground crew. In these instances, if, after subsequent review of outside hospital and/or ground crew documentation, it is determined that the subject did not meet inclusion criteria and/or met exclusion criteria, the subject will remain enrolled in the study based on the intention-to-treat principle.

In the event that a verbal report must be used in lieu of physical documentation or directly witnessing the qualifying vitals, documentation of the verbal report will serve as the source documentation for determining eligibility. Verbal reports will be documented in the air medical record and will detail the information reported and by whom.

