6. POTENTIAL RISKS AND BENEFITS

6.1 POTENTIAL RISKS

Risks Associated With LTLR-WB: The whole blood product to be utilized starting in the prehospital environment in the pilot clinical trial is the identical product to be used in the hospital and identical to the current whole blood product that has been transfused in over 200 patients over the last 24 months at the University of Pittsburgh without evidence of complications or transfusion reactions. The primary risk with LTLR-WB is a hemolytic transfusion reaction which will be followed as an important secondary outcome. There have been no hemolytic transfusion reactions in over 200 patients transfused LTLR-WB at the University of Pittsburgh in the last 24 months. The primary risks with any blood transfusion can be found in the Circular of Information prepared jointly by AABB, the American Red Cross, America's Blood Centers, and the Armed Services Blood Program. Those primary acute immunologic complications include hemolytic transfusion reactions, immune mediated platelet destruction, febrile nonhemolytic reactions, allergic reactions, anaphylactoid reactions and transfusion-related acute lung injury (TRALI). Delayed immunologic complications include delayed hemolytic reaction, alloimmunization, posttransfusion purpura, transfusion-associated graft-vs-host disease. Nonimmunologic complications include transmission of infectious agents, bacterial sepsis, transfusion-associated circulatory overload (TACO), hypothermia and metabolic complications.

The primary risk associated with transfusion of Rh+ blood into a woman of child-bearing potential (WCP) is hemolytic disease of the fetus and newborn (HDFN) of a future pregnancy. Complications of HDFN include fetal anemia, fetal hydrops, and in the most severe cases, fetal death. However, the overall risk of poor fetal outcome in a future pregnancy for Rh- women that are administered Rh+ blood products has been estimated to be less than 0.5%⁹⁰. Of note, the incidence of a female being Rh- is only 15%. This means that the majority of WCP are at no risk of Rh mismatch. For those WCP that are at risk, the likelihood of poor fetal outcome is very small.

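### Predefined subgroup 1 sets women over 50 against a group that contains them and leaves eligible women aged 18–49 out of both sides, so no predefined analysis gives a separate estimate for them

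*Combined protocol and SAP*

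**What the plan says.** Section 2.8 (Predefined Subgroup Analyses) lists eight subset analyses of the primary safety/efficacy and feasibility outcomes. The first is "Females > 50 years of age versus study cohort with females < 50 years excluded". The other seven concern in-hospital transfusion, brain injury, scene or referral origin, early operation, anticoagulant or antiplatelet history, massive transfusion and prehospital red cells. None uses sex or age.

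Eligibility has no sex restriction. The age exclusion in section 3.3 reads "Documented age: Age ≥90 or <18 years of age", and the only exclusion related to child-bearing is part of "Known prisoner or known pregnancy". Section 6.1 discusses younger women as recipients of the study product: "The primary risk associated with transfusion of Rh+ blood into a woman of child-bearing potential (WCP) is hemolytic disease of the fetus and newborn".

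Aim I (section 1.2) begins "Determine the feasibility and most appropriate study population that will lead to a large multicenter clinical trial". Section 2.9 sets the status of the subgroups: "Subgroup analyses will be exploratory and be based on baseline factors specified prior to the initiation of the trial".

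**The concern.** A subgroup comparison needs groups that do not overlap, and it should place every enrolled patient somewhere unless the plan says why not. Subgroup 1 fails on both counts. It is also the only predefined subset that uses sex or age, so what it leaves out is not picked up elsewhere.

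The omitted patients matter to a stated aim. Whether younger women belong in the larger trial is a population question that the protocol itself brings up, by using Rh-positive blood and discussing the risk for women of child-bearing potential. A pilot meant to inform the choice of population would be expected to report, at least descriptively, accrual and mortality by arm for the group whose inclusion is in question.

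**Working it through.** **Design figure.** The documents state no figure for subgroup 1. The trial's one design figure, power of 0.800921 with drift 2.81024 (section 2.9), does reproduce: 0.22 / √(2 × 0.22 × 0.78 / 56) = 2.8102, and the two stated boundaries then give power of 0.801. The present point does not depend on it.

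**Who is on which side.** Sections 3.2 and 3.3 admit both sexes aged 18–89. Taking the definition literally, with age in whole years:

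| Eligible patients | Left side (women > 50) | Right side (cohort without women < 50) |
|---|---|---|
| Men | no | yes |
| Women over 50 | yes | yes |
| Women aged exactly 50 | no | yes |
| Women aged 18–49 | no | no |

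The left side is a subset of the right, the age-50 boundary is treated differently on the two sides, and one eligible group appears on neither.

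**Effect of the overlap if the sides are compared directly.** Let A be the outcome proportion in women over 50, C the proportion in the rest of the right-hand group (men and women aged exactly 50), and f the share of women over 50 in the right-hand group. The right-hand proportion is B = fA + (1 − f)C, so

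A − B = (1 − f)(A − C).

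The documents give no sex-by-age split, so f is an assumption. With equal variances, the correlation between the two estimates is √f.

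| Assumed f | A − B as a multiple of A − C | Correlation of the two estimates |
|---|---|---|
| 5% | 0.95 | 0.22 |
| 10% | 0.90 | 0.32 |
| 20% | 0.80 | 0.45 |
| 30% | 0.70 | 0.55 |

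The identity is exact for a difference in proportions. For a difference between treatment effects it is exact only if f is the same in both arms, and approximate otherwise.

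**How many patients are left out.** The share of women aged 18–49 is also not given. Of the planned 112 patients, an assumed 5% is 0.05 × 112 = 5.6, about 6, and an assumed 25% is 0.25 × 112 = 28.

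**What a corrected subgroup could show.** With k women split evenly over the arms (h = k/2 per arm) and the design rates of 33% and 11%, the 95% half-width for the arm difference is 1.96 × √((0.11 × 0.89 + 0.33 × 0.67) / h) = 1.96 × √(0.319 / h).

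- k = 6, h = 3: half-width 0.64, power about 9%.
- k = 28, h = 14: half-width 0.30, power about 28%.

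Against a design difference of 0.22, such a group can be described but not tested usefully.

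**The case against.** The best defence is that the list announces analyses within subsets. Items 5 and 6 name a single subset with no comparator, so item 1 may mean two separate analyses, each comparing arms: one in women over 50 and one in the cohort without women under 50. No test of interaction or of a difference between subgroups is specified in section 2.8, section 2.9 or the Appendix 8 tables. This stands as far as it goes. A reader might infer that the overlap necessarily pulls a result towards the null, but that happens only if the two sides are compared directly. Even then the factor (1 − f) is a fixed rescaling, and a test that allowed for the correlation would be unaffected. The word versus favours the direct comparison but does not settle it. On either reading, women under 50 are absent.

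A reader might also infer that these women are lost to the trial, or that Aim I cannot be informed at all. The documents do not support that. Section 2.9 keeps all enrolled patients in the intention-to-treat analysis, and the cohort without younger women is itself one candidate population. If counts by arm were reported for both, the figures for women under 50 would follow by subtraction. The plan does not call for that side-by-side report, so this softens the gap without closing it.

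Third, the Rh risk in section 6.1 concerns a future pregnancy. Neither 28-day mortality nor accrual can measure it, so a corrected subgroup would not address it either.

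Finally, the item might be taken as a leftover from an eligibility rule that excluded younger women. The current text states no such rule, and the point does not need one.

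**Conclusion.** The definition of subgroup 1 is wrong as written. Under a direct comparison it is not a valid subgroup contrast; under the two-subset reading it is an incomplete pair. Both readings leave eligible women aged 18–49 without a separate predefined estimate, and both leave the age-50 boundary inconsistent. These conclusions follow from the text alone.

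The sizes rest on assumptions. Shrinkage to 0.95–0.70 of the disjoint difference assumes f of 5–30% and applies only to a direct comparison. The 6–28 omitted patients assume that women aged 18–49 are 5–25% of 112.

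The consequence is modest. The subgroup is exploratory, the primary analysis is untouched, and a corrected version would be imprecise. It is still worth correcting, because a stated rule is defective, it bears on a stated aim, and the correction costs very little.

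**What to change.** Rewrite item 1 in section 2.8 as disjoint groups that cover every enrolled patient, using the protocol's own cut-point: women under 50 versus all other patients or, if preferred, women under 50, women aged 50 or over, and men. In each group report the arm difference in 28-day mortality with a 95% confidence interval, and the feasibility outcomes, labelled exploratory and descriptive. If the result without younger women is also wanted, keep it as a labelled sensitivity analysis beside the full intention-to-treat result.

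The cost is a short edit. Age and sex are already collected for Table 1 of Appendix 8, so no added data or patients are needed. There are two drawbacks. The groups will be small, with wide intervals. And section 2.9 calls for subgroup factors fixed before the trial starts, while the documents do not show whether Version 7 precedes enrolment; the change should be dated and marked as made after initiation if enrolment has begun.

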2.4 INTERVENTIONAL ARM

Prehospital Phase Interventional Arm: Two units of LTLR-WB (O+) will be stored at each helicopter base in temperature regulated blood bank approved refrigerators for up to 14 days, which is the period within which cold stored platelets are thought to retain maximal function. Two units of LTLR-WB will be transported on all air medical flights with prehospital staff in blood banking approved and verified coolers. The temperature of the blood will be monitored throughout transit and storage in accordance with standard blood banking and Stat MedEvac procedures. Following 14 days without use, LTLR-WB will be replaced with new LTLR-WB units and the old products will be returned to the blood bank for recycling into PRBCs.. During transport, storage and during all flights standard STAT MEDEVAC protocols for storing and carrying blood products at the base and on the helicopters will be followed. While at the bases the blood units are stored in a dedicated blood refrigerator and moved to cooler for transport only when the aircraft is launched. The blood is packaged in the coolers with a thermometer for temperature maintenance to assure that they are maintained at 2-5 degrees Celsius at all times. The Clinical Protocol that is currently followed and will be followed for all blood products in the study can be found in Appendix 1. Our FDA approved blood bank will follow all regulations required by the FDA for safe blood and blood component transfusion. On day 15, after ensuring the WB unit had remained in temperature compliance and is otherwise eligible for recycling according to 21 CFR 640.2(c), the WB unit will be recycled into a PRBC unit following the standard operating procedures at the Centralized Transfusion Service in Pittsburgh.

Patients who meet all inclusion and no exclusion criteria at the scene, at a referral hospital or during transport and are randomized to the interventional arm will receive up to 2 units of LTLR-WB (O+) en-route to a PPOWER participating trauma center based upon hemodynamic status using identical criteria as the Prehospital Standard of Care arm. If the intervention is completed during transport, standard operating procedures for the prehospital setting will be employed by the prehospital providers during the remaining flight. (Appendix 7)

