2.5 STANDARD OF CARE ARM

Prehospital Standard Care Arm: Patients who meet all inclusion and no exclusion criteria at the scene, at a referral hospital or during transport and are randomized to the standard of care arm of the study will receive resuscitation fluids, including crystalloid and PRBC infusion, per the current standard practice.

In-Hospital Standard Care Arm: Once enrolled in the standard of care arm, prehospital providers will inform the trauma team of PPOWER enrollment and standard of care arm

assignment upon arrival and on-going in-hospital blood component transfusion will be at the discretion of the trauma attending/team based upon the hemodynamic status of the patient, injury severity, need for therapeutic intervention, control of hemorrhage and on-going coagulopathy. Patients enrolled in the standard of care arm will receive products using a balanced component transfusion strategy (1:1:1 - fresh frozen plasma: packed red blood cells: platelets)²² with TEG directed adjustment if blood products are required for on-going

Fig 2. Schematic depicting randomization arm comparison

resuscitation.⁸² Four units of uncrossmatched PRBCs will be available for urgent release in the emergency department. (**Figure 2**)

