2.6 RANDOMIZATION

Procedures Assuring Adherence to Randomized Assignment: Enrollment will occur in the prehospital phase of the trial and LTLR-WB or prehospital standard of care will be provided based upon randomization assignment. Prehospital providers will designate the patient as enrolled and notify receiving staff of the treatment arm. Research staff will be present upon arrival and will communicate directly with blood banking staff/anesthesia and the trauma team regarding the randomization arm of the patient. Once in-hospital, LTLR-WB randomized patients may receive LTLR-WB transfusion as indicated during this acute resuscitation phase of in-hospital care up to 6 units in-hospital and 8 units of LTLR-WB total.

Randomization and Blinding: A single stage cluster randomization scheme will be utilized. Designated air medical bases at the University of Pittsburgh will be block randomized and assigned to the LTLR-WB arm or Standard of Care (control) arm for 1 month time intervals. The cluster design will be at the level of the helicopter base. The block scheme will vary randomly between 2 and 4 month block sizes over the period of enrollment for the trial. Randomization assignments will be determined prior to the start of the bases enrollment following the above single stage cluster design using standard computerized randomization software. Communication with the blood bank transportation services and each respective air base will occur and an annual schedule of randomization assignment will be distributed to each study air base. This specific randomization scheme is required due to the limited supply of O+ LTLR-WB and also due to the logistics and delivery of the intervention in the prehospital setting. The

proposed pilot trial will be an open label trial as blood product transfusion requires appropriate documentation and essential look back procedures.

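### The list of predefined subgroups includes three defined by events after arrival and one (prehospital PRBC) that is partly arm-dependent, against the plan's own rule that subgroups rest on baseline factors

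*Combined protocol and SAP*

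**What the plan says.** Section 2.9 states the rule twice, under the secondary clinical outcomes and under the statistical distributions: "Subgroup analyses will be exploratory and be based on baseline factors specified prior to the initiation of the trial".

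Section 2.8 (Predefined Subgroup Analyses) lists eight subgroups, to be applied to the primary safety/efficacy and feasibility outcomes. Items 1 (sex and age), 3 (head injury severity), 4 (scene or referral hospital) and 6 (preinjury anticoagulant or antiplatelet therapy) describe the patient or the injury. The other four are:

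- "2) Patients who ultimately did or did not require in-hospital blood transfusion"
- "5) Patients that require operative intervention in the first 24 hours"
- "7) Patients who ultimately did or did not require massive transfusion"
- "8)Patients who did or did not receive prehospital PRBCs"

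The arm is fixed before the patient is met. Section 2.6 says that air medical bases "will be block randomized and assigned to the LTLR-WB arm or Standard of Care (control) arm for 1 month time intervals". Section 2.5 says that control patients "will receive resuscitation fluids, including crystalloid and PRBC infusion, per the current standard practice". Section 2.4 gives LTLR-WB patients up to two units in flight, "based upon hemodynamic status using identical criteria as the Prehospital Standard of Care arm", with standard prehospital procedures once those units are used.

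The only counting rule is in Section 2.8 (Clinical Outcome Definitions). It treats each transfused LTLR-WB unit as one PRBC, one FFP and one platelet pack, but it sits inside the item on requirements over the first 24 hours of admission.

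**The concern.** A subgroup supports a treatment-effect comparison only if membership cannot be altered by treatment. Items 2, 5 and 7 are settled in hospital, after the prehospital product has been chosen. Items 2 and 7 rest on transfusion requirement, which is itself a secondary outcome (Section 2.8) and which Section 6.3 says whole blood may reduce.

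Item 8 is more awkward because it can split patients on part of the treatment contrast. Read literally, a control patient who meets the in-flight trigger and is given red cells falls in the PRBC stratum. A similar patient in the other arm, given LTLR-WB on the same criteria, falls in the no-PRBC stratum. The no-PRBC comparison then sets controls who did not need blood against a whole-blood arm that still holds many who did.

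The stake is interpretation. Section 6.4.2 has the DSMB monitor a priori subgroups, and Specific Aim I is to identify the most appropriate population for the multicenter trial. A distorted stratum could inform either. This kind of bias does not shrink with more patients, so it would persist if the list were carried into the larger trial.

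**Working it through.** **1. The plan's own figure.** The subgroup section states no number. The nearest is the power in Section 2.9 (56 per arm, 33% versus 11%). The pooled drift is 0.22 / sqrt(0.22 × 0.78 × 2/56) = 2.810 (plan: 2.81024). With the printed boundaries, two-look power is 0.8010 (plan: 0.800921). It reproduces, and nothing below alters it.

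**2. Classification.**

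| Item | When membership is settled | Baseline? |
|---|---|---|
| 1, 4, 6 | Before treatment | Yes |
| 3 | Scored after arrival, but describes the injury | Yes |
| 2, 5, 7 | In hospital, after assignment | No |
| 8 | Before air-crew contact or in flight; not separated | Mixed |

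**3. Item 8, no-PRBC stratum, no true effect, LTLR-WB not counted as PRBC.** Let p be mortality in both arms, s the share of controls given PRBC, w the share of the LTLR-WB arm given PRBC, and RR the mortality ratio of patients who need red cells to the others.

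- Control mortality without PRBC: m0 = p / (1 + s(RR − 1))
- LTLR-WB mortality without PRBC: m1 = (p − w·RR·m0) / (1 − w)
- Spurious difference: m1 − m0 = m0 (RR − 1)(s − w) / (1 − w)

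The difference is positive (against whole blood) only if RR > 1 and s > w. It is exactly zero when s = w.

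From the documents: p = 0.33 and 56 per arm (Section 2.9). Assumed, because no PRBC rates are given: s = 0.2 to 0.5, RR = 1.25 to 2.5, w from 0 up to s.

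| s | RR | w | m0 | m1 | Difference (points) |
|---|---|---|---|---|---|
| 0.5 | 2.5 | 0 | 0.33/1.75 = 0.189 | 0.330 | 14.1 |
| 0.4 | 1.75 | 0 | 0.33/1.30 = 0.254 | 0.330 | 7.6 |
| 0.4 | 1.75 | 0.2 | 0.254 | 0.301 | 4.8 |
| 0.4 | 1.75 | 0.3 | 0.254 | 0.281 | 2.7 |
| 0.4 | 1.75 | 0.4 | 0.254 | 0.254 | 0 |
| 0.2 | 1.25 | 0.1 | 0.33/1.05 = 0.314 | 0.323 | 0.9 |
| 0.2 | 1.25 | 0.2 | 0.314 | 0.314 | 0 |

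With p = 0.30, the overall mortality in Section 2.2, the top of the range is 12.9 points.

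**4. Against sampling error.** The Wald 95% half-width is 1.96 × sqrt(m0(1 − m0)/(56(1 − s)) + m1(1 − m1)/(56(1 − w))), ignoring clustering by base. For w up to 0.10 it is 17.7 to 21.3 points. At s = w = 0.5 and RR = 1.25 it reaches 23.8, where the bias is zero. The largest bias is 14.1 / 19.0 = 0.74 of its half-width.

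**5. Sensitivity to the model.** A second model lets one latent severity drive both death and need for blood. Its assumptions are that 30% to 60% need at least one unit, 2% to 10% need more than two, the odds ratio for death is 1.5 to 2.5 per SD, and the severity–need correlation is 0.6. PRBC use is lower in the LTLR-WB arm throughout. It gives 1.6 to 9.4 points against whole blood in the no-PRBC stratum and 3.4 to 21.2 in the PRBC stratum. The PRBC stratum would hold about 17 to 34 controls and 1 to 6 LTLR-WB patients.

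**6. If LTLR-WB counts as a red-cell unit.** With equal need and equal practice, both differences are 0. If whole-blood crews transfused 55% to 65% against 45% in control (assumed), the second model gives about 1 to 3 points in favour of whole blood. Counting therefore removes the built-in imbalance, but item 8 remains post-assignment in an open-label trial.

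**The case against.** The strongest reply is that the harm from item 8 depends on a reading the plan does not fix. Item 8 does not say who gave the PRBC. Patients also come from referral hospitals, and units given there before air-crew contact precede the study treatment. The conversion of LTLR-WB to PRBC is broadly worded and is the only counting rule available; if it reaches prehospital units, the bias is near zero. No subgroup test or decision rule is specified, the analyses are labelled exploratory, and the size rests on assumed inputs and on the model.

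Most of this stands. A reader might infer that all four items are plainly non-baseline, or that item 8 must be biased against whole blood by at least a point. The documents support neither. Item 8 is mixed, and a non-zero minimum appears only if PRBC use in the LTLR-WB arm is capped by assumption (at 10%, for example). PRBC given at a referral hospital, or under standard procedures after the LTLR-WB units are used, could exceed any such cap.

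What does not stand is exploratory status as a full answer: the sentence that calls the subgroups exploratory also requires baseline factors. Items 2, 5 and 7 break that requirement on any reading.

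It can also be said that item 1 has a flaw of its own, since its comparator still contains the women over 50. That is true but separate; item 1 is still defined by baseline data.

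**Conclusion.** The plan contradicts itself. Three predefined subgroups (2, 5, 7) are not baseline factors, and a fourth (8) is a mixture that the text does not separate. This part needs no assumptions.

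The bias in item 8 is conditional. It requires that LTLR-WB not be counted as PRBC, that PRBC use be lower in the LTLR-WB arm, and that recipients die more often. Then the no-PRBC stratum leans against whole blood, by 0 to about 14 points in the mixture model. That is within the stratum's sampling error, so a significant pilot result from this cause alone is unlikely. For items 2 and 7 bias is plausible but unquantified; for item 5 it is not shown.

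A reader might go further and infer that the trial's main conclusion is at risk. It is not: the primary comparison uses all enrolled patients by assignment, and its alpha and sample size do not depend on these strata. The change should be made because it costs little and the list may guide the DSMB and the next trial.

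**What to change.** In Section 2.8:

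- Limit the treatment-effect subgroups to items 1, 3, 4 and 6.
- Move items 2, 5, 7 and 8 to a separate list labelled post-assignment and descriptive, not to be read as treatment-effect subgroups. Descriptive use for the feasibility outcomes can stay.
- State that a prehospital LTLR-WB unit counts as a red-cell unit when item 8 is tabulated.

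Give the DSMB the same split for its monitoring under Section 6.4.2. The rule in Section 2.9 can then stand as written.

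Do not add a new subgroup, such as PRBC given before air-crew contact, once enrolment has started unless it is labelled post hoc. Section 2.9 requires factors specified before the trial begins.

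Cost: between-arm effect claims are lost in four exploratory strata, and a protocol amendment is needed. Under Section 6.4.2 (Study Changes), that means IRB approval, NIH Program Officer and DSMB approval if the change is judged significant, and review of whether it needs prospective FDA submission. No new data or patients are required.
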